4.4.2.5 Overall Survival

A secondary efficacy endpoint is overall survival (OS). OS is defined as the time from randomization to death from any cause.

Data for patients who are not reported as having died at the time of analysis will be censored at the date last known to be alive. Data for patients who do not have post-baseline information will be censored at the date of randomization. OS will be analyzed for the Treated Patients Population and in the IA Treated Patients Population at interim analysis.

Kaplan-Meier methodology will be used to construct survival curves for each treatment arm and to estimate median OS for each treatment arm. The Brookmeyer-Crowley

methodology will be used to construct the 95% CI for the median OS for each treatment arm (Brookmeyer and Crowley 1982).

The Kaplan-Meier approach will also be used to estimate 6-month OS rate in each arm, along with 95% CI calculated using Greenwood's formula. 12-month OS rate in each arm will also be provided as appropriate.

Duration of survival follow-up will be summarized for all patients in the analysis using descriptive statistics (median, range). Duration of survival follow-up is defined as the survival time for all patients in the analysis (whether a patient is alive or has died).

4.4.3 Disease Control Rate Disease control rate is defined as the proportion of patients with either confirmed objective response (CR or PR observed on The methodologies described for the analysis of confirmed ORR will be used for the analysis of DCR (except the formal treatment comparison with the historical reference that will not be performed on DCR

4.4.3.2 Investigator-assessed Objective Response Rate (confirmation required)

Investigator-assessed ORR, is defined as the proportion of patients with a confirmed objective response, either CR or PR, observed on two consecutive assessments \geq 4 weeks apart with the use of RECIST v1.1, based on the investigator assessment. The methodologies described for the analysis of confirmed ORR will be used for the analysis of investigator-assessed ORR (except the formal treatment comparison with the historical reference that will not be performed on investigator-assessed ORR).

4.4.3.3 Assessment of Tumor Burden

Changes over time in the sum of longest diameters (SLD) for target lesions identified by the IRC will be plotted for each patient by visit for each treatment arm.

4.4.3.4 Best change from baseline in tumor burden (% SLD)

A summary of the best percent change from baseline, defined as the smallest percent change observed post-baseline, in the sum of longest diameters (SLD) for target lesions, according to the IRC, will be presented by treatment arm.

A waterfall plot or vertical bar chart of observed best percent change from baseline ordered from highest (i.e., largest increase) to lowest (i.e., largest decrease) by patient will be presented for each treatment arm.

4.4.4 Crossover Analyses

4.4.4.1 Confirmed Objective Response Rate after Crossover

Confirmed ORR after crossover is defined as the proportion of patients with a confirmed objective response during the post crossover period, either complete response (CR) or partial response (PR), observed on two consecutive assessments ≥ 4 weeks apart with the use of RECIST v1.1, based on IRC assessment.

The tumor assessment just preceding crossover will serve as a re-baseline scan against which all subsequent scans will be compared. Confirmed ORR after crossover will be analyzed for the Crossover Patients, Treated Patients Population.

The methodologies described for the analysis of confirmed ORR will be used for the analysis of confirmed ORR after crossover (except the formal treatment comparison with the historical reference that will not be performed on confirmed ORR after crossover).

Duration of response will also be provided and the methodology will be the same as used for the analysis of the IRC DOR.

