2.3 INTERIM AND PRIMARY ANALYSIS TIMING

2.3.1 **Primary Analysis Timing**

The analysis of confirmed ORR for

The primary analysis of confirmed ORR will be performed once all patients have been enrolled and a minimum follow-up of approximately 6 months after the second tumor assessment, or approximately 9 months after randomization, has been achieved among the patients, who remain in follow-up for ORR assessment, whichever is earlier.

will be conducted after all

enrolled Chinese patients have had a minimum follow-up of approximately 6 months after the second tumor assessment, or approximately 9 months after randomization, has been achieved among the patients, who remain in follow-up for ORR assessment, whichever is earlier.

3. STUDY CONDUCT

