4.1.3 IA Treated Patients Population

The IA Treated Patients Population is defined as all patients randomized at least 5 months prior to the interim analysis CCOD that have received at least any dose of study treatment. Analysis by treatment arm performed on the IA Treated Patients Population will be grouped according to the actual treatment received. The IA Treated Patients Population will be used at interim analysis for the efficacy analysis.

4.1.4 Crossover Population

The Crossover Patients, Treated Patients Population or Safety Population is defined as all patients randomized to the atezolizumab monotherapy arm that crossed-over to the tiragolumab in combination with atezolizumab arm, and received at least any dose of tiragolumab after cross-over but not prior to cross-over.

4.1.5 Pharmacokinetic-Evaluable Population

The Pharmacokinetic-Evaluable Population is defined as all patients who received any dose of study treatment and who have at least one post-baseline PK sample available.

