4.4 EFFICACY ANALYSIS

4.4.1 Primary Efficacy Endpoint

4.4.1.1 Objective Response Rate (confirmation required)

The primary efficacy endpoint is confirmed objective response rate (ORR), defined as the proportion of patients with a confirmed objective response, either complete response (CR) or partial response (PR), observed on two consecutive assessments \geq 4 weeks apart with the use of RECIST v1.1, based on IRC assessment.

In the primary efficacy analysis, patients without any post-baseline tumor assessments will be considered non-responders. Confirmed ORR will be analyzed for the Treated Patients Population at primary analysis. Confirmed ORR will be analyzed for the IA Treated Patients Population at interim analysis.

A one-sample z-test for proportion will be used to compare the confirmed ORR of the tiragolumab in combination with atezolizumab arm to the historical reference (see Section 2.2.2). No formal treatment comparison will be performed between the two arms or between the atezolizumab monotherapy arm and the historical reference.

An estimate of the confirmed ORR and its 95% CI will be calculated for each treatment arm using the Clopper-Pearson method.

In order to characterize responders, descriptive statistics (e.g. median, range) will be provided for time from randomization to response (TTR) for patients with an objective response.

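### Confirmed ORR after crossover has no minimum time since crossover, so late crossovers count as non-responders and the descriptive rate is biased modestly downward

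*SAP*

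**What the plan says.** Section 4.4.4.1 defines the endpoint: "Confirmed ORR after crossover is defined as the proportion of patients with a confirmed objective response during the post crossover period". The response must be seen by the IRC on two consecutive assessments at least 4 weeks apart. The reference scan is reset: "The tumor assessment just preceding crossover will serve as a re-baseline scan against which all subsequent scans will be compared". The denominator is given as follows: "Confirmed ORR after crossover will be analyzed for the Crossover Patients, Treated Patients Population".

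Section 4.1.4 defines that population as patients randomized to monotherapy who crossed over and "received at least any dose of tiragolumab after cross-over but not prior to cross-over". It sets no condition on time since crossover. Neither 4.1.4 nor 4.4.4.1 shows a gap or blacked-out text that could hold one.

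Section 4.4.4.1 also carries over the primary method: "The methodologies described for the analysis of confirmed ORR will be used for the analysis of confirmed ORR after crossover", apart from the test against the historical reference. The primary method (4.4.1.1) includes the rule that "patients without any post-baseline tumor assessments will be considered non-responders".

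Elsewhere the SAP does protect maturity. The interim population (4.1.3) takes "all patients randomized at least 5 months prior to the interim analysis CCOD". The primary analysis (2.3.1) waits for "a minimum follow-up of approximately 6 months after the second tumor assessment, or approximately 9 months after randomization", whichever is earlier. Section 2 allows crossover after unequivocal progression on monotherapy and names no latest date. Scans are 6-weekly (±7 days) for 48 weeks from Cycle 1 Day 1 and 9-weekly after that (Appendix 2).

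**The concern.** A patient with no post-crossover scan is a non-responder by rule. A patient with only one cannot meet the two-scan definition. Both stay in the denominator, so the error goes one way: the reported rate is too low whenever some patients cross over close to the cutoff. The existing follow-up rules do not prevent this, because their clocks start at randomization or the second scan and secure no time after crossover.

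At stake is the SAP's only response-rate estimate for adding tiragolumab after progression on atezolizumab alone. As specified, it would move with the choice of cutoff date even if the drug effect did not. If the follow-up condition is not fixed beforehand, the denominator may be chosen after the results are known.

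**Working it through.** The SAP gives no figure for this endpoint, so there is none to reproduce.

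**1. Time needed to confirm** (Appendix 2 schedule)
- 6-weekly scans: 2 × 6 = 12 weeks after the re-baseline scan.
- 9-weekly scans: 2 × 9 = 18 weeks.
- Scan windows or an unscheduled scan can shorten this somewhat, so 12 weeks is the normal figure and not a strict bound.

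**2. Time available to the last patient randomized** (section 2.3.1)
- Second scan at week 12 plus 6 months (26.1 weeks) = about 38 weeks.
- 9 months = about 39 weeks. The earlier applies: about 38 weeks.
- 38 − 12 = 26. If this patient crosses over after about week 26, she has under 12 weeks left. If she crosses over at week 8, she has about 30.

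**3. Number of patients** (section 2)
- About 160 randomized 3:1 gives 160 × 1/4 = 40 on monotherapy, so at most about 40 crossovers in the global phase.

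**4. Share with under 12 weeks at the primary cutoff**

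The inputs are assumptions, since the SAP gives no accrual period or monotherapy progression times:
- time to progression exponential with median 2, 3 or 4.5 months, rounded up to the next 6-weekly scan;
- crossover 0.5 month later;
- follow-up from randomization uniform from 9 to 9 + A months, with accrual A = 6, 10 or 14 months;
- every monotherapy patient crosses over if she progresses before the cutoff, and there are no deaths.

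Simulating 400,000 patients per setting, the share of crossovers with under 12 weeks runs from about 2% (14-month accrual, median 2 months) to about 13% (6-month accrual, median 4.5 months). Time is counted here from crossover. Counted from the re-baseline scan, half a month earlier, the shares are somewhat lower.

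A wider set (accrual 26 to 78 weeks, median 8.7 to 26 weeks) gives 1.9% to 16.0%.

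**5. Effect on the rate**

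Reported rate = true rate × (1 − share affected), taking the true rate as unrelated to when the patient crossed over. For an assumed true rate of 15%:

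| Share affected | Reported rate |
|---|---|
| 2% | 15% × 0.98 = 14.7% |
| 13% | 15% × 0.87 = 13.1% |
| 16% (wider set) | 15% × 0.84 = 12.6% |

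With an assumed 20 crossovers, the expected missed responders are 20 × 0.15 × 0.02 = 0.06 to 20 × 0.15 × 0.13 = 0.39.

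**6. Scale against sampling error** (Clopper-Pearson 95% intervals, illustrative counts)
- 3/20 = 15.0% (3.2% to 37.9%).
- With 2 of the 20 set aside as immature, 3/18 = 16.7% (3.6% to 41.4%).

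**The case against.** The strongest reply is that the bias is trivial. It amounts to less than half an expected responder in 20 crossovers, against an interval more than 30 percentage points wide, for a descriptive estimate in at most about 40 patients. An all-treated denominator also matches the SAP's primary approach, and duration of response after crossover handles short follow-up by censoring. All of that stands and sets the severity. It does not remove the one-sided error: censoring of duration does nothing for the response rate, and the primary analysis has a maturity rule that this endpoint lacks.

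A reader might infer more than the SAP supports in three ways.

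- **Using 5 months as the threshold.** The same simulation puts 7% to 29% of crossovers under 5 months. That is not the share affected, because a patient between 12 weeks and 5 months can be confirmed on the 6-weekly schedule. Some later responses could still be missed in that range, but the SAP gives nothing from which to size this.
- **Applying it to an interim cutoff.** With a 5-month minimum from randomization, 13% to 30% would have under 12 weeks and 35% to 64% under 5 months. Section 4.4.4.1 does not specify an interim crossover analysis, whereas the ORR, DOR, PFS and OS sections each name the interim population. These figures carry no weight here.
- **Applying 18 weeks to everyone.** The 9-weekly schedule starts only after Week 48. In the simulation 1% to 12% of crossovers fall after that. The SAP does not say whether the schedule restarts at crossover.

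**Conclusion.** The point holds as a minor one. Sections 4.1.4 and 4.4.4.1 together count patients who have not had time for a confirmed response as failures, and no other rule in the SAP corrects for it. The direction follows from the definitions alone, provided some patients cross over within about 12 weeks of the cutoff (about 18 on the later schedule), which nothing in the SAP prevents.

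The size rests on assumed accrual, progression times, crossover lag and a 15% true rate. On those assumptions about 2% to 13% of crossovers are affected, and the reported rate falls to between 14.7% and 13.1%. The number of crossovers is unknown; if it is small, one or two late crossovers matter more than these averages suggest.

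It would be wrong to read this as a threat to the trial's main result. The only hypothesis test compares the doublet arm with the historical reference and does not use post-crossover responses.

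**What to change.** In section 4.4.4.1:

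1. Keep the estimate in all crossover patients.
2. Add beside it the confirmed ORR, with its Clopper-Pearson interval, among patients whose re-baseline scan was early enough before the cutoff to allow two scheduled post-crossover assessments under the schedule that applies to them. Select by dates only, regardless of outcome, so that patients who die or drop out early remain as non-responders.
3. Report post-crossover follow-up time and the number of immature patients.

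The cost is one or two sentences and one derived flag. The added estimate has a slightly smaller denominator and a wider interval, and it under-represents late crossovers, who spent longest on monotherapy. That is why it should stand beside the all-patients rate and not replace it.

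A 5-month restriction on the headline rate, borrowed from the interim population, is not advised. It would discard patients who can be evaluated and tilt the estimate further toward early progressors.

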4.4.4.2 Analysis of Overall Survival Accounting for Crossover

The impact of subsequent crossover for patients in the atezolizumab arm on OS will be assessed depending on the number of patients who crossover to atezolizumab plus tiragolumab. If more than 10% of patients in the atezolizumab arm crossover, the following analyses may be performed:

- OS will be discounted according to a range of possible effects on OS of subsequent crossover (e.g. 10%, 20%, 30%, 40%, 50%).
- Additional sensitivity analyses may be conducted if deemed necessary.

4.4.5 Sensitivity Analyses

Sensitivity analyses will also be performed for the primary endpoint of confirmed ORR to check the robustness of the primary results.

Confirmed ORR will be estimated for each treatment arm among all treated patients without major exclusion/inclusion criterion protocol deviation (also excluding patients without measurable disease at study entry, according to the IRC) and that are PD-L1

positive per		according to gla	ss reads or	nly of the		. Confirmed		
ORR will als	ORR will also be estimated among the ITT Population.							
- "			1.000					
Furthermore	e, at interin	n analysis, confir	med ORK	wiii be ana	alyzed for the	e IA Treated		
Patients Pop	oulation (s	ee Section 4.4.1	.1).					

4.4.6 **Subgroup Analyses**

The consistency of confirmed ORR results in subgroups defined by demographics (age, race/ethnicity, geographic regions), baseline disease characteristics (histology, prior bevacizumab use, maximal extent of disease, PD-L1 expression level) and stratification factors (ECOG performance status, prior use of (chemo) radiotherapy, treatment history) will be examined. Summaries of confirmed ORR by subgroup will be provided.

Kaplan-Meier plots of PFS and OS will also be produced for selected subgroups.

4.5 PHARMACOKINETIC AND PHARMACODYNAMIC ANALYSES

PK samples of tiragolumab and atezolizumab will be collected in this study.

Tiragolumab and atezolizumab serum concentration data (minimum serum concentration and maximum serum concentration) will be tabulated and summarized.

Descriptive statistics will include means, medians, ranges, and standard deviations, as appropriate.

Additional PK analyses will be conducted, as appropriate, based on the availability of data. These additional analyses may not be included in the CSR for this study.

4.6 SAFETY ANALYSES

Unless specified otherwise, safety analyses described below will be conducted for the Safety Population (see Section 4.1.3).

Patients will be grouped into two categories:

- atezolizumab monotherapy
 - Patients that received at least one dose of atezolizumab and never received any dose of tiragolumab.
 - Information from patients originally randomized to atezolizumab monotherapy; that received at least one dose of atezolizumab prior to crossover and received a dose of tiragolumab after crossover; safety information up until the first dose of tiragolumab treatment will be included.
- tiragolumab in combination with atezolizumab
 - Patients originally randomized to tiragolumab in combination with atezolizumab that received at least one dose of tiragolumab.
 - Patients randomized to atezolizumab monotherapy that received a dose of tiragolumab (due to a medication error) prior to an eventual crossover.

Information after the start of tiragolumab, for patients randomized to atezolizumab that received a dose of tiragolumab after crossover, will be reported in separate safety analysis. Only selected safety analysis will be performed on this Crossover Patients, Safety Population.

4.6.1 Exposure to Study Medication

Study drug exposure, including treatment duration, number of cycles, and dose intensity, will be summarized for each treatment arm for atezolizumab and for tiragolumab with descriptive statistics.

4.6.2 Adverse Events

Verbatim description of adverse events will be mapped to Medical Dictionary for Regulatory Activities (MedDRA) thesaurus terms. Adverse events will be graded by the investigator according to the NCI CTCAE v5.0. Treatment-emergent adverse events will be summarized by mapped term, appropriate thesaurus level, NCI CTCAE grade and treatment arm. Multiple occurrences of the same event will be counted once at the maximum grade. All reported AEs, SAEs, Grade 5 AEs, treatment-related AEs (as assessed by the investigator), severe AEs (Grade ≥ 3), immune-mediated AEs (imAEs), imAEs requiring the use of systemic corticosteroids, AEs leading to study drug discontinuation, and AEs leading to interruption or reduction will be summarized.

Listings of AEs will include all treatment-emergent AEs.

Deaths and cause of death will be summarized by treatment arm overall, as well as, during the study treatment period, and those reported during the follow-up period after treatment discontinuation.

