2. STUDY DESIGN

Study WO42017 is a randomized, Phase II, global, multicenter, open-label study designed to evaluate the efficacy and safety of tiragolumab plus atezolizumab and atezolizumab monotherapy in patients with metastatic and/or recurrent PD-L1-positive cervical cancer after progression or recurrence from at least one platinum-based but no more than two prior systemic therapies.

Approximately 160 patients will be randomized in this study global enrollment phase in a 3:1 ratio. Additional patients may be subsequently randomized in a

. Women with Eastern Cooperative Oncology Group (ECOG) Performance Status of 0 or 1 who have metastatic and/or recurrent PD-L1–positive cervical cancer are eligible (refer to protocol synopsis in Appendix 1 for complete eligibility criterion).

In the doublet arm, patients will receive atezolizumab at a fixed dose of 1200 mg administered by IV infusion Q3W on Day 1 of each 21-day cycle, followed by tiragolumab at a fixed dose of 600 mg administered by IV infusion Q3W also on Day 1 of each 21-day cycle.

In the atezolizumab monotherapy arm, patients will receive atezolizumab at a fixed dose of 1200 mg administered by IV infusion Q3W on Day 1 of each 21-day cycle.

Treatment may be continued as long as patients are experiencing clinical benefit, as assessed by the investigator, in the absence of unacceptable toxicity or symptomatic deterioration attributed to disease progression after an integrated assessment of radiographic data, biopsy results (if available), and clinical status. Patients who meet the criteria for equivocal disease progression per RECIST v1.1 will be permitted to continue treatment (tiragolumab in combination with atezolizumab or atezolizumab alone) if they meet all of the following criteria:

- Evidence of clinical benefit, as assessed by the investigator
- Absence of symptoms and signs (including worsening of laboratory values indicating unequivocal progression of disease)
- No decline in ECOG Performance Status that can be attributed to disease progression

[figure not shown]
 Absence of tumor progression at critical anatomical sites (e.g., leptomeningeal disease) that cannot be managed by protocol-allowed medical interventions

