Crossover is allowed from the atezolizumab monotherapy arm to the tiragolumab plus atezolizumab arm after unequivocal progressive disease has been recorded during atezolizumab monotherapy, at the discretion of the investigator and after consultation with the Medical Monitor.

The primary study objectives are to make a preliminary assessment of efficacy of tiragolumab in combination with atezolizumab and atezolizumab monotherapy, as measured by independent review committee (IRC)-determined confirmed objective response rate (ORR), and to evaluate safety.

The study schema is provided in Figure 1.

Figure 1 Study Schema

- Stratification factors:
- ECOG Performance Status (0 vs. 1)
- Prior use of chemoradiotherapy or radiotherapy (yes vs. no)
- Treatment history (persistent vs. recurrent disease)

1L=first-line; CDx=companion diagnostic; ECOG=Eastern Cooperative Oncology Group; PD-L1=programmed death-ligand 1; Q3W=every 3 weeks; R=randomization; s/p= status post.

Note: Crossover is allowed from the atezolizumab monotherapy arm to the tiragolumab plus atezolizumab arm after unequivocal progressive disease has been recorded during atezolizumab monotherapy, at the discretion of the investigator and after consultation with the Medical Monitor.

[figure not shown]

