4.1.6 Safety Population

The safety population is defined as patients who received at least one dose of tiragolumab or atezolizumab. The Safety Population is identical to the Treated Patients Population (see Section 4.1.1) and will be used for the safety analysis.

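### As written, the cut at first tiragolumab dose also governs the overall and follow-up death summaries, so crossover patients count in the monotherapy denominator but cannot count there as deaths

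*SAP*

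**What the plan says.** Section 2 of the SAP sets the arm sizes ("Approximately 160 patients will be randomized in this study global enrollment phase in a 3:1 ratio") and permits the switch: "Crossover is allowed from the atezolizumab monotherapy arm to the tiragolumab plus atezolizumab arm after unequivocal progressive disease has been recorded".

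Section 4.6 divides patients into two safety categories. A patient who crosses over belongs to the atezolizumab monotherapy category, but for her "safety information up until the first dose of tiragolumab treatment will be included". What follows is handled apart: "Information after the start of tiragolumab, for patients randomized to atezolizumab that received a dose of tiragolumab after crossover, will be reported in" a separate safety analysis. That analysis is limited: "Only selected safety analysis will be performed on this Crossover Patients, Safety Population". The SAP does not list which outputs are selected.

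Section 4.6.2 then specifies the death table: "Deaths and cause of death will be summarized by treatment arm overall, as well as, during the study treatment period", and also for the follow-up period after treatment discontinuation. It does not mention crossover patients.

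**The concern.** Ending a crossover patient's monotherapy record at her first tiragolumab dose is sensible for adverse events, because later events arise under a different exposure. It does not suit a death summary that is labelled overall and extends into follow-up. A patient must be alive to receive that dose, so within the information kept for the monotherapy column she is always a survivor. Section 4.6 states no matching cut for patients randomized to the doublet.

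The patients affected are also not a random part of the arm, since crossover requires unequivocal progression. Section 2 lists evaluation of safety among the primary objectives. A by-arm death and cause-of-death table that runs low in one column could be read as showing more deaths on the combination, and it would not match the deaths counted for overall survival.

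**Working it through.** **How the rules combine**

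1. Denominator. Section 4.1.6: "The Safety Population is identical to the Treated Patients Population (see Section 4.1.1) and will be used for the safety analysis". Crossover patients were treated with atezolizumab, so they are in this population, and Section 4.6 places them in the monotherapy category.
2. Numerator. The crossover population in Section 4.1.4 consists of monotherapy patients who "received at least any dose of tiragolumab after cross-over but not prior to cross-over". They were alive at the cut, so any death falls after it and outside the information kept for the monotherapy category.
3. Doublet column. Section 4.6 includes patients randomized to the doublet who received tiragolumab, and monotherapy patients given tiragolumab in error before crossover. Deaths after crossover are in neither group; they go to the separate analysis.
4. Exceptions. Neither Section 4.6 nor Section 4.6.2 states one for deaths.

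**Size**

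The SAP gives no figure to reproduce here. It also gives no crossover rate and no death rate, so both are assumptions. The 10% in Section 4.4.4.2 is only the trigger for optional overall survival analyses and not a forecast.

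- Arm sizes: 160 at 3:1 gives 160 × 1/4 = 40 monotherapy and 160 × 3/4 = 120 doublet patients, taking all as treated. The percentages below do not depend on these numbers.
- c = fraction of the monotherapy arm that crosses over; d = true death proportion, taken as equal in crossover and other patients and in both arms.
- Death proportion shown for monotherapy = (1 − c) × d. Shortfall = d − (1 − c) × d = c × d.

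| d | c | All deaths, monotherapy | Shown under the cut | Doublet, same risk | Shortfall (points) |
|---|---|---|---|---|---|
| 40% | 10% | 16/40 (40%) | 14.4/40 (36.0%) | 48/120 (40%) | 4.0 |
| 40% | 25% | 16/40 (40%) | 12.0/40 (30.0%) | 48/120 (40%) | 10.0 |
| 40% | 50% | 16/40 (40%) | 8.0/40 (20.0%) | 48/120 (40%) | 20.0 |
| 50% | 10% | 20/40 (50%) | 18.0/40 (45.0%) | 60/120 (50%) | 5.0 |
| 50% | 25% | 20/40 (50%) | 15.0/40 (37.5%) | 60/120 (50%) | 12.5 |
| 50% | 50% | 20/40 (50%) | 10.0/40 (25.0%) | 60/120 (50%) | 25.0 |
| 60% | 10% | 24/40 (60%) | 21.6/40 (54.0%) | 72/120 (60%) | 6.0 |
| 60% | 25% | 24/40 (60%) | 18.0/40 (45.0%) | 72/120 (60%) | 15.0 |
| 60% | 50% | 24/40 (60%) | 12.0/40 (30.0%) | 72/120 (60%) | 30.0 |

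If crossover patients die at a different rate, the shortfall is c times their own death proportion. For example, take c = 50%, an arm average of 60%, and crossover mortality at 0.8 of that average. The uncounted deaths are 40 × 0.5 × 0.8 × 0.6 = 9.6, the column shows (24 − 9.6)/40 = 36%, and the shortfall is 24 points. It can shrink, but it cannot change sign.

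**The case against.** The strongest reply is that *overall* already means every death among the arm's patients, whatever the period, and that the cut on safety information was never meant to reach deaths found in survival follow-up. That is a possible reading, and on it the bias does not arise. But Section 4.6.2 does not say so, and Section 4.6 sets its grouping without excepting deaths. On that reading the two sections conflict, and the text still needs changing.

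Other parts of the reply stand and limit the point:

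- A reader might infer that post-crossover deaths disappear from the trial's results. They do not. Overall survival (Section 4.4.2.5) counts death from any cause from randomization with no cut at crossover. The separate crossover analysis may also show these deaths, although the SAP does not name them among its selected outputs. Overall survival does not supply cause of death.
- A reader might infer harm to the trial's main conclusion. The only hypothesis test is doublet response rate against the 14.6% reference. The synopsis defines the safety endpoint as incidence and severity of adverse events. The death table is descriptive, and no decision rule depends on it.
- A reader might infer a gap that is certain to be large. With no crossover or death rate in the SAP, the low end of the range is as admissible as the high end.
- Grouping by exposure is deliberate in Section 4.6, and a separate crossover column would also show these deaths. Unless the monotherapy denominator were changed to match, however, that column's percentage would still be too low.

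**Conclusion.** The point holds for the overall and follow-up death and cause-of-death summaries in Section 4.6.2. Followed as written, they understate monotherapy mortality by about c × d, or 4 to 30 points under the assumed 10–50% crossover and 40–60% deaths. If true risk is equal in the two arms, this appears as an excess of deaths on the doublet. The direction follows from the rules; the size rests entirely on the assumed rates. If the overall row was intended to override the cut, the defect is an unreconciled conflict between Sections 4.6 and 4.6.2. The response-rate test and overall survival are untouched. The change should be made, but the trial's primary efficacy conclusion does not depend on it.

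**What to change.** In Section 4.6.2:

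- Exempt the overall and follow-up death and cause-of-death summaries from the cut at first tiragolumab dose.
- Count all deaths of crossover patients up to the data cut-off (CCOD) under their original monotherapy group, with sub-rows for deaths before first tiragolumab dose and deaths after crossover.
- Keep the cut for adverse events and on-treatment deaths.

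In Section 4.6, name deaths and cause of death among the selected outputs for the crossover safety population.

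The cost is about one sentence in each section and two sub-rows in the table. Deaths are already collected for overall survival. The drawback is that the monotherapy overall row will include deaths after tiragolumab exposure; the sub-rows make these visible.
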